Bimatoprost SR 10 µg	Dose strength: 10 µg	Sham administration procedure
	Eye drops: Vehicle BID	Eye drops: Timolol BID
Bimatoprost SR 15 µg	Dose strength: 15 µg	Sham administration procedure
	Eye drops: Vehicle BID	Eye drops: Timolol BID
Control	Sham administration procedure	Sham administration procedure
	Eye drops: Timolol BID	Eye drops: Timolol BID

BID = twice daily

The patients will begin self-administration of the study-provided eye drops (vehicle or timolol) in both eyes, starting with the evening dose on the first administration (Bimatoprost SR or Sham administration) day visit. Patients will continue self-administration of the study-provided eye drops in the morning (08:00 ± 1 hour) and in the evening (20:00 ± 1 hour) approximately 12 hours apart throughout the study, with the exception of the morning of a subsequent visit, on which the morning eye drop administration will be performed at the study site.

Randomization/Stratification: Randomization to treatment groups will use a 1:1:1 ratio (Bimatoprost SR 10 µg:Bimatoprost SR 15 µg:Control). Randomization will be stratified by baseline study eye Hour 0 IOP (≤ 25 mm Hg or > 25 mm Hg).

Visit Schedule: Patients who complete the entire study without receiving nonstudy IOP-lowering medication in both eyes will have a minimum of 25 visits and 6 phone calls. [REDACTED]

[REDACTED]

Patients who have not received nonstudy IOP-lowering medication (prohibited prior to Week 52) in both eyes will receive a repeat administration of Bimatoprost SR (or Sham administration in Control group study eyes and all fellow eyes) at the Week 16 and Week 32 visits as indicated. Administration should not occur if the investigator believes that there are any safety concerns. Patients who have received nonstudy IOP-lowering medication in both eyes will be followed for at least 12 months following the last administration of Bimatoprost SR or Sham, at which time they may exit early at the investigator’s discretion.

Study Population Characteristics

Number of Patients: Approximately 600 patients will be enrolled in the study.

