The investigator is strongly encouraged not to use prohibited medications as outlined in Section 4.5.2. In order to maintain masking in the event that nonstudy IOP-lowering medications (prohibited prior to Week 52 unless required for a safety reason and attested to by the investigator) are administered, if a patient is started on a nonstudy IOP-lowering medication in only one eye, the patient will continue to use the study-provided eye drops in that eye as directed. The nonstudy IOP-lowering medication will be prescribed by the investigator according to local standard of care practices and used in addition to the study-provided eye drops in that eye. The eye not receiving a nonstudy IOP-lowering medication will continue to receive the study-provided eye drops as directed. If the eye receiving the nonstudy IOP-lowering medication is a Bimatoprost SR study eye, the eye will receive Sham administration on the administration day(s). If the eye receiving the nonstudy IOP-lowering medication is a Control group study eye or a fellow eye, the eye will continue to receive Sham administration on the administration day(s). If both eyes are receiving nonstudy IOP-lowering medications, the patient will discontinue use of the Allergan

study-provided eye drops and will not receive additional Bimatoprost SR or Sham administration (see Section 5.6.1). However, as described in Section 8.8, the patient will still remain in the study and be followed for 12 months following their last administration of Bimatoprost SR or Sham.

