5.6.1 Treatment Regimen/Dosage Adjustments

Patients who have received nonstudy topical IOP-lowering medication (prohibited before Week 52 unless required for safety reasons due to inadequate IOP control and attested to by the investigator) in a Bimatoprost SR study eye will receive Sham administration in that eye on the Bimatoprost SR repeat administration day(s). Patients who have received nonstudy topical IOP-lowering medication in a fellow eye or a Control Group study eye will continue to receive Sham administration in that eye on the administration day(s).

Patients who have received nonstudy IOP-lowering medication in both eyes will not undergo Bimatoprost SR administration or Sham administration in either eye.

Patients who use nonstudy IOP-lowering medication (prohibited before Week 52 unless required for safety reasons due to inadequate IOP control and attested to by the investigator) in only one eye will be followed for the duration of the study. If used in both eyes, patients will be followed at minimum for 12 months after the last administration of Bimatoprost SR or Sham. Patients using nonstudy IOP-lowering medications in both eyes prior to the Week 16 or Week 32 Administration Day will not attend the administration visit(s), nor will they attend the Day 2, Days 4 and 8 (phone call), or 2-week visits (ie, Weeks 2, 18, and 34) following an administration. They would continue the schedule at Week 22 or Week 38, as appropriate for the administration cycle.

Patients who have received nonstudy IOP-lowering medication in both eyes before the time of the Month 14 visit are not required to attend the Month 14 or 18 visits unless the visit is 12 months after their last injection or Sham, at which time the patient may exit early and should complete all Month 20/Exit visit examinations. Patients who have received nonstudy IOP-lowering medication in both eyes by the time of the Month 16 visit are not required to attend the Month 18 visit, unless that visit is 12 months after their last injection or Sham, at which time the patient may exit early and should complete all Month 20/Exit visit examinations.

For patients who have not received nonstudy IOP-lowering medications by the time of study discontinuation or completion, poststudy evaluations regarding the need for IOP-lowering medications should be conducted according to the treating physician's clinical opinion.

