5.10 Retreatment

Administration of Bimatoprost SR will occur at fixed intervals of 16 weeks, up to a total of 3 administrations. Patients will be readministered the Bimatoprost SR dose strength to which they were randomized unless in the investigator's opinion it would not be in the best interest of the patient to readminister Bimatoprost SR based on previous adverse events or safety concerns. Patients who have been treated with nonstudy IOP-lowering medication in only one eye will still attend administration visits; if the treated eye is the Bimatoprost SR study eye, the patient will receive a Sham administration in that eye. Control group study eyes and fellow eyes that have been treated with nonstudy IOP-lowering medications will continue to receive Sham administrations. Patients who have been treated with nonstudy IOP-lowering medication in both eyes will not attend the Administration Day visits, nor will they attend the Day 2, Days 4 and 8 (phone call), or the 2-week visits (ie, Weeks 2, 18, and 34) following an administration.

6. Response Measures and Summary of Data Collection Methods

Detailed information on equipment and methodology to be used is provided in the Protocol Procedure Manual.

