4.0 INTRODUCTION

This statistical analysis plan (SAP) provides a more technical and detailed elaboration of the statistical analyses of the efficacy and safety data for Study 192024-091. Specifications of tables, figures, and data listings are contained in a separate document.

Study 192024-091 is a Phase 3, multicenter, randomized, masked, parallel-group comparison, active-controlled, repeat administration study in patients at least 18 years of age who have been diagnosed with open-angle glaucoma (OAG) or ocular hypertension (OHT).

The length of the study will be approximately 22 months for each patient, consisting of screening of up to 28 days before washout, washout period of up to 42 days before initial administration of study medication, 52-week treatment period, plus 8 months extended follow-up. Signed informed consent from the patient or the patient's legally authorized representative will be obtained before any study-related procedures are begun. All patients who provide informed consent will be assigned a subject number. Patients meeting all inclusion and no exclusion criteria will be randomized in a 1:1:1 ratio to receive 1 of 2 dose strengths of Bimatoprost SR treatment (Bimatoprost 10 µg or 15 µg plus vehicle twice daily [BID] eye drops) or control treatment (Sham administration procedure plus timolol BID eye drops) in the study eye on Day 1. The randomization will be further stratified by baseline study eye Hour 0 IOP (≤ 25 mm Hg or > 25 mm Hg). Patients who have not received non-study IOP-lowering medication in both eyes will receive a repeat administration of Bimatoprost sustained release (SR) or control treatment in the study eye at the Week 16 and Week 32 visits.

[figure not shown]
All patients will be masked to their treatment group. Treatment groups are shown as follows:

Treatment	Study Eye Treatment	Fellow Eye Treatment
Bimatoprost SR 10 µg	Dose strength: 10 µg Eye drops: Vehicle BID	Sham administration procedure Eye drops: Timolol BID
Bimatoprost SR 15 µg	Dose strength: 15 µg Eye drops: Vehicle BID	Sham administration procedure Eye drops: Timolol BID
Control	Sham administration procedure Eye drops: Timolol BID	Sham administration procedure Eye drops: Timolol BID

[figure not shown]
BID = twice daily

[figure not shown]

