Prior and concomitant medications will be separately summarized using the safety population for each treatment group as the number and percentage of patients under each indication preferred term (MedDRA) and unique base preferred name from the World Health Organization Drug Dictionary Enhanced (WHODDE).

Concurrent procedures will be provided in the listings.

Non-study IOP Lowering Medications/Procedures

A non-study IOP-lowering medication is defined as a medication for which the investigator specifically marked “Yes” to the question “Is this medication used as a non-study IOP-lowering medication?” on the concomitant medication electronic case report from (eCRF). A non-study IOP-lowering procedure is defined as a procedure for which the investigator specifically marked “Yes” to the question “Was this an IOP-lowering procedure?” on the concurrent procedure eCRF.

Other medications or procedures that could potentially reduce IOP but are not marked in the eCRF as non-study IOP-lowering medications/procedures will be listed in the separate document used to identify data excluded from the PP analysis.

Washout Ocular Medication

Similarly, washout ocular medications will be tabulated by treatment group for the study eye and pooled for the fellow eye.

9.0 **EXTENT OF EXPOSURE AND TREATMENT COMPLIANCE**

9.1 **EXTENT OF EXPOSURE**

Throughout the study, each patient will receive up to 3 administrations of Bimatoprost SR or Sham injection in each eye with a fixed interval of 16 weeks. The number and percentage of patients receiving Bimatoprost SR or Sham treatment in the study eye during the study will be tabulated by the number of treatment administrations for each treatment group.

Each patient's study duration will be calculated as the number of days between the exit date and Day 1 Administration Day, inclusively (date of the exit - Day 1 Administration date + 1). Patients' study duration will be summarized using descriptive statistics for each treatment group.

10.0 **EFFICACY ANALYSES**

The primary efficacy variable for country/regions other than US will be time-matched IOP change from baseline in the study eye. The primary efficacy variable for the United States (US) Food and Drug Administration (FDA) (Division of Transplant and Ophthalmology Products) is IOP in the study eye (Section 10.3.1).

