11.0 SAFETY ANALYSES

The safety analysis will be performed using the safety population. The safety parameters will include the following nonocular safety parameters: nonocular AEs, clinical laboratory values, vital signs, and pregnancy; [REDACTED]

[REDACTED] Unless otherwise stated, the last nonmissing safety assessment before the first dose of study treatment will be used as the baseline for all analyses of that safety parameter. Continuous variables will be summarized by number of patients and mean, SD, median, the 1st quartile and the 3rd quartile, minimum, and maximum values. Categorical variables will be summarized by number and percentage of patients.

[REDACTED]

For all safety by-cycle summary analyses, in order to compare cycles of similar duration, the data included in each cycle will be,

- Cycle 1 (16 weeks): data from the 1st injection to the 2nd injection date -1 or upper bound of week 15 visit window (section 16.1) if a patient didn't receive the 2nd injection;
- Cycle 2 (16 weeks): data from the 2nd injection to the 3rd injection date -1 or upper bound of week 31 visit window (section 16.1) if a patient didn't receive the 3rd injection;
- Cycle 3 (20 weeks): data from the 3rd injection to upper bound of week 52 visit window (section 16.1);
- Extended safety follow up: data after week 52 for patients with 3 injections and extended follow up.

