11.1 ADVERSE EVENTS

Adverse events will be coded by SOC and preferred term using the Medical Dictionary for Regulatory Activities.

For a given AE and patient, if more than 1 severity grade is reported, the worst severity grade (the greater of the onset and maximum severity recorded on the electronic case report from [eCRF]), will be used for analysis.

Adverse events will be classified into ocular AEs and nonocular AEs. An ocular AE will be determined as indicated on the AE form of eCRF, and thus are not limited to AEs with primary SOC of eyes. The treatment-related ocular AEs will be further broken down by either related to injection procedure or related to study drug as indicated on eCRF. Ocular AEs will be tabulated by treatment group for the study eye and pooled for the fellow eye, and nonocular AEs will be summarized by treatment group for patient. Analysis by cycle of treatment will also be performed.

Treatment-Emergent Adverse Events

An AE will be considered a treatment-emergent adverse event (TEAE) for the study treatment period if the AE meets 1 of the following criteria:

- The onset date is on or after the first study treatment date.
- The onset date is before the first study treatment date and either:
 - The severity of the event worsened on or after the first treatment date.
 - The event became serious on or after the first study treatment date.

An AE will be considered as a TEAE for a treatment cycle if the AE meets 1 of the following criteria:

- The onset date is on or after the treatment administration of the cycle but prior to the next cycle administration.
- The onset date is before the treatment administration of the cycle and either:
 - The severity of the event worsened on or after the treatment administration of the cycle.
 - The event became serious on or after the treatment administration of the cycle.

Overall summary of TEAEs will be provided on a per-patient basis for categories of all TEAEs, treatment-related TEAEs, injection procedure-related TEAEs, study drug-related TEAEs, serious TEAEs (STEAEs), deaths, and TEAEs leading to study discontinuation. Each category (except deaths) will be further classified into ocular and nonocular subcategories.

The number and percentage of patients reporting TEAEs will be provided on a per-patient basis by 1) SOC and preferred term; 2) SOC, preferred term and severity in descending order of frequency for each treatment group.

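### SAP 9.1 and the by-cycle safety rules do not separate Bimatoprost SR implants from Sham given to rescued SR-group study eyes, so read literally they overstate repeat-implant exposure

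*SAP*

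**What the plan says.** **What a rescued eye receives.** Protocol 5.10 covers patients with only one eye on non-study IOP-lowering medication: "if the treated eye is the Bimatoprost SR study eye, the patient will receive a Sham administration in that eye". Protocol 5.3 and 5.6.1 state the same rule, and the patient stays in follow-up. The case of both eyes is different (Protocol 5.6.1): "Patients who have received nonstudy IOP-lowering medication in both eyes will not undergo Bimatoprost SR administration or Sham administration in either eye".

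**Exposure.** SAP 9.1 gives counts and percentages within every group: "patients receiving Bimatoprost SR or Sham treatment in the study eye during the study will be tabulated by the number of treatment administrations". The same section also uses the term injection for the Sham procedure.

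**By-cycle safety.** SAP 11.0 starts each cycle at an injection; Cycle 2, for example, holds "data from the 2nd injection to the 3rd injection date -1". SAP 11.1 ties a cycle's treatment-emergent events to the administration: "The onset date is on or after the treatment administration of the cycle but prior to the next cycle administration". Neither section says whether injection or administration includes Sham. Ocular events in the study eye are shown by treatment group.

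**Who is repeated.** The Protocol Summary (Visit Schedule) reads "Patients who have not received nonstudy IOP-lowering medication (prohibited prior to Week 52) in both eyes will receive a repeat administration of Bimatoprost SR", followed by a bracket for Sham eyes and the qualifier that this is done as indicated. SAP 4.0 sets the same both-eyes condition and says that patients meeting it "will receive a repeat administration of Bimatoprost sustained release (SR) or control treatment in the study eye at the Week 16", with the same again at Week 32.

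**The concern.** Safety after initial and repeated administrations is a stated study objective, and the exposure and by-cycle tables are where a reader will look for evidence on repeat implants. If Sham procedures in SR-group study eyes are counted together with implants, two things follow. The exposure table shows more patients with two or three implants than there were. The SR columns for Cycles 2 and 3 hold eyes that received no implant in that cycle.

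The second matters most for events caused by the procedure. Sham is needleless and does not enter the anterior chamber (Protocol 5.9.3). In the Phase 1/2 study most adverse events fell within the first 2 days after administration and were attributed to the procedure (Protocol 1.3.3). SAP 11.1 plans tables aimed at that signal: procedure-related ocular events, events within and beyond 2 days of administration in each cycle, and events leading to implant removal by cycle.

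**Working it through.** **1. Plan's own figures.** The documents state no exposure count, study-eye-only rescue rate or adverse-event rate that could be reproduced here. The only usable size is the planned number per group: 540/(1 − 0.10) = 600 enrolled, or 200 per group, with 180 expected to remain (200 × 0.90). This reproduces. I use 180 as an illustrative number of SR-group eyes attending a repeat administration; the 10% loss is stated for the first 12 weeks only.

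**2. Counting rule applied to the possible sequences** (fellow eye not rescued):

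| SR-group study eye: Day 1, Week 16, Week 32 | Implants received | Count under SAP 9.1 read literally |
|---|---|---|
| SR, SR, SR | 3 | 3 |
| SR, SR, Sham | 2 | 3 |
| SR, Sham, Sham | 1 | 3 |

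A patient rescued in both eyes has no later administration, so nothing is miscounted.

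**3. By-cycle membership.** Control study eyes receive only Sham. They can have a Cycle 2 or 3 only if Sham counts as an injection or administration, and SAP 9.1 already uses injection for Sham. The natural reading therefore places a switched SR eye in its SR group's Cycle 2 or 3. If injection meant SR only, Control would have no Cycles 2 and 3. A switched eye's by-cycle data would also stop at the Week 15 or Week 31 window, through the SAP 11.0 rule for a missing next injection. The cycle-completer definition (SAP 7.0) and the extended follow-up definition (SAP 11.0, patients with three injections) depend on the same undefined word.

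**4. Does the as-treated rule settle it?** Protocol 7.1 bases the safety analysis on the treatment a patient actually received. That works per patient and does not say where to put an eye whose treatment changes between cycles.

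**5. Size.** Let f be the share of SR-group eyes at a repeat administration that receive Sham. Overstatement of the implant count = f/(1 − f). Reported rate = (1 − f) × p_SR + f × p_Sham. All values of f, p_SR and p_Sham are assumptions; p_SR is set at 10%.

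| Assumed f | Sham / SR eyes of 180 | Overstatement | Rate if p_Sham = 0% | If 10% | If 15% |
|---|---|---|---|---|---|
| 2% | 4 / 176 | 2.3% | 9.8% | 10.0% | 10.1% |
| 5% | 9 / 171 | 5.3% | 9.5% | 10.0% | 10.3% |
| 10% | 18 / 162 | 11.1% | 9.0% | 10.0% | 10.5% |
| 20% | 36 / 144 | 25.0% | 8.0% | 10.0% | 11.0% |

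Eyes are rounded to whole numbers; in the first row 2% of 180 is 3.6, taken as 4, and the unrounded formula gives 0.02/0.98 = 2.0%. The rate falls only where p_Sham is below p_SR.

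**The case against.** The strongest defence is that SAP 9.1 can be read arm by arm: SR administrations in the SR groups, Sham in Control. The Protocol Summary uses a similar shorthand, with Sham bracketed for Control study eyes and fellow eyes. In the same way, injection could mean SR in the SR arms, and the rule for a missing second injection would then keep a switched eye out of Cycle 2. Table specifications are in a separate document, and text near the cycle definitions is redacted.

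Part of this stands. The by-cycle point rests on an undefined word and on visible text only, so it deserves moderate confidence. The arm-by-arm reading, however, is stated nowhere, and the SR-only reading of injection creates the problems in step 3 of the working. Either way the SAP needs an edit.

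The defence is right on three further points:

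- **General dilution.** A reader might infer that all SR adverse-event rates in Cycles 2 and 3 are diluted. The documents do not support that. A switched eye has had at least one implant, more than 75% matrix degradation is expected only within about 12 months (Protocol 1.3), and the eye now takes added IOP-lowering medication. Its rate for other ocular events could equal or exceed that of re-implanted eyes.
- **Masking of a rising risk.** A reader might infer that a real rise in risk with repeat implants would be hidden. That needs a high switch rate and a large SR-to-Sham risk ratio, and the documents give neither. The Phase 1/2 count of patients who had not needed added medication by Week 16 (62 of 67) is deleted text in the amendment log. It pools dose groups and does not identify study-eye-only rescue, so it is not used. Before Week 52, rescue is also restricted to safety need, attested for each eye (Protocol 4.5.2).
- **Selection.** Limiting the SR columns to re-implanted eyes would condition on post-randomisation rescue in the SR arms but not in Control.

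The conflict over who is re-implanted should not be overstated either. SAP 4.0 includes control treatment, which could cover Sham, and the Protocol Summary adds its qualifier.

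**Conclusion.** The concern holds in a limited form. Read literally, SAP 9.1 overstates how many SR patients received two or three implants, because Sham given to a rescued SR study eye counts as an administration. On the natural reading of SAP 11.0 and 11.1 the same eyes enter the SR denominators in Cycles 2 and 3. There, rates of injection-procedure-related, within-2-day and repeat-implant events would be expected to come out too low; for other ocular events the direction is uncertain.

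The size cannot be fixed from the documents. The 2.3% to 25% overstatement rests on an assumed switched share of 2% to 20% of 180 eyes. Only patients rescued in the study eye alone before Week 16 or Week 32 contribute.

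A reader might also suspect the efficacy results. They are not touched: the primary comparison is at Week 12, before any repeat administration, and IOP values after rescue are excluded (SAP 10.1). Cycle 1 and whole-study safety counts by treatment group are also unaffected.

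**What to change.** 1. **SAP 9.1:** tabulate the number of Bimatoprost SR implants actually administered to the study eye (1, 2, 3), with Sham administrations to SR-group study eyes in a separate row.
2. **SAP 11.0 and 11.1:** state whether injection and administration include Sham, and use the same definition for cycle completers (SAP 7.0) and extended follow-up.
3. **By-cycle ocular events:** keep the tables by treatment group. Add a presentation by the treatment actually given to the study eye in that cycle, with Sham-converted SR eyes in their own column.
4. **Reconcile** the Protocol Summary and, less clearly, SAP 4.0 with Protocol 5.3, 5.6.1 and 5.10 on what a patient rescued only in the study eye receives. The review takes no position on which rule should apply.

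Cost: SAP wording and one derived flag, since administration dates (Protocol 10.4.1) and kit numbers (Protocol 5.9) are already recorded. The added presentation has smaller denominators, and it must be labelled descriptive because it selects on post-randomisation rescue.
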